NH Resident Data will be collected for consented NH residents from Brief interview of family/friends (see attachment), NH staff interview of the resident (see attachment), NH staff ratings (clinical global assessments of change in overall sleep quality and sleep-related conditions - see Appendix; NH staff sleep reports - see attachment); through primary data collection (actigraph/Fitbit measurements; these are wristwatch-sized devices worn on the wrist); through medical records (age, diagnoses, medical history, and medications); and through NH secondary data from the Minimum Data Set (MDS; all Medicare-reimbursed NHs are required to collect MDS assessments on all residents; the MDS contains information on resident medical conditions, functioning, cognition, psychotropic and pain/analgesic medication use, activities of daily living decline, and sleep-, mood-, and activity-related items). Table 1 summarizes the primary and secondary outcomes and data sources.

NH Staff Data: staff interview data will be collected via audiorecorded qualitative interview (see Appendix).

Data Collection Procedures:

NH Resident Primary Research Data Collection: will consist only of actigraph/fitbit data.

We will measure total sleep time (TST) with data from Micro-Mini Motionlogger Actigraphs (Ambulatory Monitoring Inc., Ardsley, NY).[87] We will define nighttime as 10pm to 6am and will compute TST as the total number of minutes asleep during a nighttime period. We will measure sleep for 7 days at each measurement period (see Figure 2) to obtain reliable measurements and will use the average TST across this period. We will also examine the following: wake after sleep onset (total number of minutes awake during nighttime), how often the resident awoke during the nighttime, sleep efficiency (the ratio of

minutes asleep to minutes awake over the period), and sleep fragmentation (an index of restlessness computed as the percentage of one-minute epochs scored as awake). Sensitivity of actigraph measurement for sleep is very good (actigraphy = sleep when polysomnography = sleep was 0.97). [88]

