The training will emphasize the importance of customized individualized care, incremental approaches to treatment changes, and how to use huddles to integrate such interventions into individualized treatment plans. For example, "decrease in nighttime interruption" does not mean never checking on the resident during the night. Staff will be trained on the importance of using small PDSA (plan-do-study-act) cycles to assure that all care changes are pursued incrementally in an individualized, customized manner. This is not about one-size-fits-all care. There is no blanket edict to not interrupt the patient for the entire night. Rather, the instruction is for the team to consider and explore ways of promoting longer periods of uninterrupted sleep, and to test these innovations in incremental trials over a period of days or weeks.

NH Staff Trained Trainers Providing Training:

After B&F Consulting has trained the NH Leadership and implementation teams, those teams will then be responsible for training others in the NH. As part of the intervention training, NH staff will be trained by their NH Leadership or implementation teams or their trained designees on proper use and placement and cleaning of actigraphs and Fitbits, verbal and behavioral signs of distress that might indicate actigraph/Fitbit-related discomfort/distress, and appropriate modification techniques to try to relieve such distress. NH staff will be informed that the devices should be removed in the unlikely event that distress behaviors are not relieved by modification techniques. NH staff will be trained on importance of NH resident autonomy, and will be engaged in a discussion of how to assess for and honor NH resident assent or lack thereof with regard to the devices.

[SELECTED REFERENCES]

25.[name] C, Farrell D, [name] B, Elliot AE, Gittell JH. A long-term care leader's guide to high performance : doing better together. Baltimore: Health Professions Press; 2018.

35.Farrell D, [name] C, [name] B. Meeting the leadership challenge in long-term care : what you do matters. Baltimore: Health Professions Press; 2011.

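### Sleep fragmentation, defined as the percentage of epochs awake, is a proportion of time awake that (with all 480 night epochs scored) rescales TST; it does not measure how sleep is broken up

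*Combined protocol and SAP*

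**What the plan says.** All the definitions are in section 3(b), under Data Collection Procedures.

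- Window and TST: "We will define nighttime as 10pm to 6am and will compute TST as the total number of minutes asleep during a nighttime period". For each 7-day measurement period the plan "will use the average TST across this period".
- Wake after sleep onset (WASO): "wake after sleep onset (total number of minutes awake during nighttime".
- Number of awakenings: listed as a measure of its own.
- Sleep efficiency: the ratio of "minutes asleep to minutes awake over the period".
- Fragmentation: "sleep fragmentation (an index of restlessness computed as the percentage of one-minute epochs scored as awake".

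No denominator is written into the fragmentation definition, and the index has no component for bouts, transitions or movement. Section 3(d) names actigraphy TST as a primary outcome, together with Fitbit sleep time.

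Elsewhere broken sleep is treated as something other than short sleep. The background in section 1(a) names low total sleep time and greater fragmentation as two forms of sleep disturbance. The intervention training text in section 3(b) asks the care team to "consider and explore ways of promoting longer periods of uninterrupted sleep".

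**The concern.** A fragmentation measure should respond to how wake is spread through the night. A percentage of epochs awake responds only to how much wake there is. A resident whose sleep is consolidated into longer runs with unchanged total sleep would therefore show no change on the measure named for that effect. A resident who gains total sleep would show a lower index even if the night stayed just as broken.

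What is at stake is the set of outcome definitions carried forward. Section 2(b) makes testing and refining the research methods a specific aim, and section 3(d) says the pilot analysis will inform revisions to the randomized trial. A list of five actigraph measures that holds roughly two pieces of information per night is best corrected at this stage.

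**Working it through.** The plan gives no numerical figure on this point to reproduce, so the check is algebra on its definitions.

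**Inputs (section 3(b)).** The window is 10pm to 6am: 8 x 60 = 480 one-minute epochs. TST is minutes asleep in the window. Assumption for steps 1 to 3: every epoch is scored asleep or awake, and the 480-epoch night is the denominator.

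**Step 1. The index.** Awake epochs = 480 - TST, so fragmentation = 100 x (480 - TST)/480 = 100 x (1 - TST/480).

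**Step 2. The neighbouring measures.** WASO = 480 - TST. Sleep efficiency = TST/(480 - TST).

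| TST (min) | Fragmentation (%) | WASO (min) | Sleep efficiency (ratio) |
|---|---|---|---|
| 240 | 50.0 | 240 | 1.00 |
| 300 | 37.5 | 180 | 1.67 |
| 360 | 25.0 | 120 | 3.00 |
| 420 | 12.5 | 60 | 7.00 |

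Fragmentation and WASO are linear in TST, so the relation also holds for 7-night averages. Sleep efficiency is a non-linear function, so its identity with TST holds night by night but not exactly for averages.

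**Step 3. Same TST, different nights.** Three constructed nights each have 360 min asleep and 120 min awake.

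| Pattern of wake | Fragmentation (%) | WASO (min) | Efficiency | Awakenings |
|---|---|---|---|---|
| One block at the start | 25.0 | 120 | 3.0 | 0 |
| One block mid-night | 25.0 | 120 | 3.0 | 1 |
| 24 awakenings of 5 min | 25.0 | 120 | 3.0 | 24 |

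Only the count of awakenings tells them apart.

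**Step 4. What the count already supplies.** Take TST 420 with 60 min awake. One 60-minute bout within sleep leaves two sleep runs, with a mean of 420/2 = 210 min. Thirty 2-minute awakenings leave 31 runs, with a mean of 420/31 = about 13.5 min. Both nights score 12.5% on the index. TST and the count together thus give mean run length, subject to how the window's edges are treated. They do not give the longest run.

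**Step 5. Other denominators.** The plan does not exclude these, so the range is shown for assumed values.

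| Minutes removed from the denominator | Counted from sleep onset, TST 360 (%) | Off-wrist epochs dropped, TST 300 (%) |
|---|---|---|
| 0 | 25.0 | 37.5 |
| 30 | 20.0 | 33.3 |
| 60 | 14.3 | 28.6 |
| 120 | 0.0 | 16.7 |

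For example, 100 x (480 - 60 - 360)/(480 - 60) = 14.3. The identity with TST breaks, but each value is still a share of time awake and would be the same however that wake was distributed.

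**The case against.** The strongest reply has four parts.

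**Interruption is measured.** A reader might infer that broken sleep goes unrecorded. The documents do not support that: section 3(b) lists how often the resident awoke, and step 4 shows that this count with TST yields mean run length. Awakenings per hour of sleep is itself the listed count divided by the listed TST. This part stands. What remains is that the measure named fragmentation is not the one that carries the information, and that nothing planned gives the longest run.

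**Exactness is conditional.** A reader might infer a correlation of exactly -1 with TST in the pilot data. That needs the full 480-epoch denominator, which the plan does not state. Off-wrist time is foreseeable, because section 3(b) has staff remove the devices if distress persists. This part also stands, but it does not turn a proportion of time awake into a measure of fragmentation.

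**The harms are not written down.** A reader might infer that a gain in TST will be presented as independently confirmed by the index, or that the choice of outcomes for the randomized trial will be misled. Section 3(d) plans ranges, variability and missing-data rates, with no hypothesis test on the index. It does plan to relate secondary outcomes and supplementary sleep data to TST, but Table 1, which it cites for these, is an attachment not reproduced in the text. Whether the index is among them cannot be established. A correlation of -1 might also expose the redundancy rather than hide it. These consequences are possible but not shown.

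**Uninterrupted sleep is not the sole target.** Section 2(b) aims at better sleep and more meaningful activity, and the training text covers several strategies. The point needs only that fragmentation is treated as distinct from sleep duration, and section 1(a) does that.

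**Conclusion.** The point holds in conditional form. With the 10pm to 6am night as denominator and all 480 epochs scored, the fragmentation index is 100 x (1 - TST/480), a linear rescaling of the primary outcome. Under the same condition WASO and sleep efficiency, as defined, are per-night functions of TST, so three of the four additional actigraph measures add nothing to it and only the awakening count does. With another denominator the equality fails, but the index still cannot register how wake is distributed. Interruption is therefore partly measured, under a different name.

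The size is modest: a non-primary descriptive measure, in a pilot expecting 57 residents, that can be recomputed later from the same epochs. It is worth correcting now because refining methods for the later trial is a stated aim.

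**What to change.** In section 3(b):

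1. Define fragmentation from the sequence of scored epochs, for example as awakenings per hour of sleep, with mean and longest uninterrupted sleep run per night, each averaged over the 7 nights. Say what counts as an awakening, how the edges of the window are treated, and how unscored epochs are handled.
2. Drop the percentage of epochs awake, or keep it labelled as TST rescaled with its denominator stated.
3. Do not present percent-awake, or WASO and sleep efficiency as now defined, as evidence separate from TST, and leave all three out of any association with TST under section 3(d).

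The cost is one or two sentences in the protocol and a short script on the actigraph epoch data that the study already downloads. No new data are needed, and nothing is added for residents or staff.

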d) Describe how data analysis will be performed (statistical tests, methods of evaluating data) and indicate the smallest group/unit for which separate reporting will occur. For studies involving a questionnaire, if data and reliability information are available, please describe or provide references. (Page numbers from a sponsor's protocol/grant may be referenced in this section).

Data analysis for this pilot study (R61 phase) will inform revisions to our upcoming randomized controlled trial (R33 phase). We will conduct a preliminary assessment of our outcome measures, particularly our primary outcomes from the actigraphy TST measurements and fitbit sleep time measurements, and secondary outcomes from the MDS and our supplementary sleep data (see Table 1). We will examine ranges, indicators of variability (change over time), and rates of missing data. We will also examine indicators by demographic characteristics (e.g., age, gender) and level of dementia severity (mild, moderate, severe). To test the sensitivity of our secondary outcomes and supplementary sleep data to individual differences in TST and change in TST, we will preliminarily examine the relationships of these with average TST and variability in TST.

For the qualitative interviews, all interviews will be audio recorded and transcribed and [name] will guide the experienced qualitative team in using a rapid appraisal template analysis,[112,113] a rigorous technique for thematically organizing and analyzing data. The analysis will identify, in particular, areas for modifications to the LOCK sleep program training. Interviews will also inform our decision of whether or not to include Fitbits as part of the subsequent randomized controlled trial (R33 phase), based on staff members' impressions of the value of Fitbits and their impressions of the feasibility of using both devices. We will also modify interview guides (see Appendix) for the next phase, as necessary.

[Selected References]

112.King N. Using templates in the thematic analysis of text. In: Essential Guide to Qualitative Methods in Organizational Research. London: SAGE Publications Ltd; 2004.

113.Beebe J. Basic Concepts and Techniques of Rapid Appraisal. Human Organization. 1995;54(1):42-51.

* * * Radioisotopes or Radiation Machines * * *

4) Radioisotopes or Radiation Machines

Please note: For projects requiring radiation procedures, please contact the UA Environmental Health and Safety Office at [name]

- a) If applicable, summarize in lay language the radiographic diagnostic and therapeutic procedures associated with this protocol. (X-ray, fluoroscopy, CT, radioactive materials, nuclear medicine, PET-CT, radiation oncology, accelerator, Cyber Knife procedures, etc.).
- b) Are the radiation procedures being performed a normal part of the clinical management for the medical condition that is under study (Standard of Care), or are the procedures being performed because the research participant is participating in this project (extra CT scans, more fluoroscopy time, additional Nuclear Medicine Studies, etc.) (Not Standard of Care)? If some procedures are Standard of Care and some are Not Standard of Care, check both boxes.

NOT STANDARD OF CARESTANDARD OF CAREIf it is not standard of
care, complete the rest of
this section. Provide the
University of Alabama
RSC approval
information below.If it is only standard of
care, skip the rest of this
section.

c) Are research-related radiation procedures limited to X-rays only?

Yes (Complete X-ray table).

No (Skip X-ray table).

d) Total Radiation Exposure (in mRems) from x-ray procedures:

To calculate radiation exposure from x-rays only, University of Alabama allows use of the Duke University Radiation Safety Committee dose estimate calculator. University of Alabama does not allow use of this website to calculate any other type of radiation exposure.

To determine the dose estimate, click on the appropriate links, below (you will be taken to the Duke University Radiation Safety Committee website). Enter the x-ray procedures into the appropriate fields of the website and click "create statement". Enter the dose estimate from the statement in the table above.

For studies involving adults, please click here.

For pediatric studies, please click here...

e) Please list all radiation procedures (including x-ray) that are research-related (not standard of care). Include the anatomical location and specify the number of times that each procedure will be conducted throughout the entire study.

NOTE: The IRB will determine if this study requires radiation safety review by the Radiation Safety Officer or the Radiation Safety Committee.

For more information on how to submit for radiation safety review, contact the Radiation Safety Officer.

* * * Drugs, Reagents, Chemicals, or Biologic Products * * *

5. Drugs, Reagents, Chemicals, or Biologic Products

| Pilot | Phase I | Phase II |
|-----------|----------|------------|
| Phase III | Phase IV | Not Phased |

a) Please list in the space below all investigational drugs, reagents or chemicals to be administered to participants during this study.

| b) | Please list in the space below all FDA approved drugs, reagents, chemicals to be administered to participants during this study. | | | | |
|--|--|---|--|--|--|
| Please read the IND Statement 1 and IND Statement 2. | | | | | |
| * * * Devices * * * | | | | | |
| 6. | Devices | | | | |
| a) | Please list in the space below all investigational devices to be used on participants during this study. | | | | |
| b) | Please list in the space below all FDA approved devices to be used on participants during this study. | | | | |
| * * * Subject Population(a-h) * * * | | | | | |
| Subject Population - In the space below, please detail the participants that you are requesting to recruit (include description of each group requested) | | | | | |
| a) | a) Expected age range of participants. (For example - 19 yrs to 90 yrs). | | | | |
| In the potential participant pool, we will include all NH residents aged >=50 years with an ADRD diagnosis. | | | | | |
| b) | i) Number to be directly solicited for this research. N/A | all res. at 3 NHs | | | |
| | ii) Number to be consented (including withdrawals or screen N/A failures) | 70 | | | |
| | iii)Number expected to complete the study. | 57 | | | |
| c) | If this is multi-center study, number of participants to complete N/A the study study-wide | 57 | | | |
| d) | If study involves review of medical or other records, number of N/A records to be reviewed. | 70 | | | |
| e) | If women, minorities, or minors are excluded, a clear compelling rationale must be provided unless not applicable. Examples for not including minors: disease does not occur in children; drug or device would interfere with normal growth and development; etc. | | | | |
| f) | 1. Inclusion of Women and Minorities Participants will be selected according the inclusion/exclusion criteria described in the methods section. We aim to recruit a sample that will be representative of the national nursing home (NH) population. Based upon the 2015 Centers for Medicaid and Medicare Nursing Home Compendium, 122 we will aim to enroll approximately 67% women and 33% men. The national figures for 2015 were: 79% White not Hispanic, 13.8% Black not Hispanic, 4.9% Hispanic, 1.6% Asian, .4% American Indian/Alaskan Native, .1% Native Hawaiian Pacific Islander, and .3% more than one race. We will make every effort to include a representative sample of minorities. Men and members of minority groups will be actively recruited during this protocol. We will use unbiased statistical analyses and proper methods of inference to estimate and compare intervention effects by sex/gender, race, and/or ethnicity. We will conduct exploratory analyses to detect any differences in intervention effect among these groups, because prior studies do not strongly indicate nor negate the existence of such effects. Inclusion of Children Children will not be included in this study. Children are unlikely to live or work in NHs and unlikely to have dementia. | | | | |
| , | individual's treating physician, those individuals answering an ad). How value about the research, and how will they be recruited (e.g., flyer, e-mail, we where recruitment materials will be located. Click "Add" to upload recruit | vill potential participants learn b posting, telephone, etc.)? State ment materials document. | | | |

Important to remember: Study Activities cannot begin until IRB approval is granted.

In the potential participant pool, we will include all NH residents aged >=50 years with an ADRD diagnosis. We include residents across the range of ADRD severity because this is consistent with the LOCK sleep program, in which staff will focus on residents with ADRD who have the greatest sleep problems without differentiating by ADRD severity. To identify participants, NH staff will use frontline staff huddles.

Research staff will recruit and consent a sample of NH staff at mid- and postimplementation for (mid-) and (post-) PHONE interviews about their experiences with the LOCK sleep program and Fitbits. NOTE: The LOCK sleep program itself comprises clinical practices common in NH QI efforts. These practices thus fall within the scope of staff positions and require no consent.

* * * Subject Population(i-I) * * *

7. Subject Population (continued)

i) Inclusion and Exclusion Criteria.

Identify inclusion criteria.

In the potential participant pool, we will include all NH residents aged >=50 years with an ADRD diagnosis. We include residents across the range of ADRD severity because this is consistent with the LOCK sleep program, in which staff will focus on residents with ADRD who have the greatest sleep problems without differentiating by ADRD severity. To identify participants, NH staff will use frontline staff huddles. NH staff will be trained to use the STOP-Bang screening tool to identify NH residents with high risk of obstructive sleep apnea (OSA) 82-84 and will be trained on appropriate procedures for referring any positively screened residents for medical evaluation

Identify exclusion criteria.

We will exclude residents with a high risk of OSA who are not being treated for OSA because actigraph measurements are inaccurate in that population.85 Staff will also exclude residents who have a persistent bilateral resting tremor or paralysis in both arms (a subset of persons with Parkinson's disease and related significant tremorcausing diagnoses), due to actigraph measurement inaccuracies.

j) Compensation. Explain the amount and schedule of compensation, if any, that will be paid for participation in the study. Include provisions for prorating payment.

N/A

k) Describe who will cover study related costs. Explain any costs that will be charged to the participant.Include provisions for prorating payment.

All study related costs will be covered by the NIA grant funding.

I) Estimate the probable duration of the entire study including data analysis and publication. This estimate should include the total time each participant is to be involved and the duration the data about the participant is to be collected. If the study is Investigator-initiated, a timeline for individual participant recruitment, follow-up, total time for participant accrual, and data analysis for the study is required.

The entire pilot study will last 1 year. Each NH resident participant will be involved in a 15 week data collection period.

* * * Subject Population(m) * * *

Research Involving Children

NOTE: Investigators, please include this information with the e-Protocol application if your research involves children. In Alabama a child is an individual less than 18 years of age unless the child is legally emancipated. If your research involves children with more than one vulnerability (e.g., children who are pregnant, incarcerated, or cognitively impaired) attach the supplementary information for that vulnerable population as well.

Minimal risk means that the probability and magnitude of the harm or discomfort anticipated in

the research are not greater in and of themselves than those ordinarily encountered in daily life of a healthy child or during the performance of routine physical or psychological exams or tests.

Section 1.

Select and complete the category that applies to your research.

Category 1 (45 CFR 46.404; 21 CFR 50.51) My research does not involve greater than minimal risk.

- a) My research falls under this category because:
- b) Describe what provisions will be made for soliciting the assent of the children, and the permission of both parents, or the legal guardian. (Permission from both parents must be obtained unless one parent/guardian is deceased, unknown, incompetent, or not reasonably available, or when only one parent/guardian has legal responsibility for the care and custody of the child). Justify reason(s) if seeking permission from only one parent.

Category 2 (45 CFR 46.405; 21 CFR 50.52) My research involves greater than minimal risk but presents the prospect of direct benefit to the individual participants.

- a) My research falls under this category because:
- b) Justify the risk(s) by explaining the anticipated benefit to the participants:
- c) Explain how the relation of the anticipated benefit to the risk is at least as favorable to the participants as that presented by available alternative approaches:

d) Describe what provisions will be made for soliciting the assent of the children, and the permission of at least one parent/guardian. (Permission from both parents must be obtained unless one parent/guardian is deceased, unknown, incompetent, or not reasonably available, or when only one parent/guardian has legal responsibility for the care and custody of the child). Justify reason(s) if seeking permission from only one parent.

Category 3 (45 CFR 46.406; 21 CFR 50.53) My research involves greater than minimal risk, and no prospect of direct benefit to individual participant, but likely to yield generalizable knowledge about the participant's disorder or condition.

- a) My research falls under this category because:
- b) Describe how the risks for participating in your research represent a minor increase over minimal risk (i.e., the children being recruited have a disorder or condition that would place them in a group other than an average healthy child; therefore, the research qualifies as a minor increment over minimal risk. This risk is slightly more than what the average healthy child would experience, but is reasonable for these participants because it is not more than they would experience or expect given their condition.).
- c) Describe how the research intervention(s)/procedure(s) present experiences to participants that are reasonably commensurate to those inherent in their actual or expected medical, dental, psychological, social, or educational situations:

- d) Explain why the intervention or procedure is likely to yield generalizable knowledge about the participants' disorder or condition, which is of vital importance for the understanding or amelioration of the participants' disorder or condition:
- e) Describe what provisions will be made for soliciting the assent of the children, and the permission of both parents/guardians. (Permission from both parents must be obtained unless one parent/guardian is deceased, unknown, incompetent, or not reasonably available, or when only one parent/guardian has legal responsibility for the care and custody of the child). Justify reason(s) for seeking permission from only one parent.

Category 4 (45 CFR 46.407; 21 CFR 50.54) My research does not fall under Category 1, 2, or 3 listed above. However, the research presents a reasonable opportunity to understand, prevent, or alleviate a serious problem affecting the health or welfare of children.

(NOTE: If your research is funded by, or funding has been sought from the Department of Health and Human Services (DHHS), Department of Education, or is FDA regulated, a report must be sent for review to the DHHS Secretary, Secretary of the US Department of Education, or Commissioner of FDA. If this category is applicable, the Office of Research Compliance will prepare and submit a report of IRB review to the appropriate federal official(s)).

a) My research falls under this category because:

b) Describe what provisions will be made for soliciting the assent of the children, and the permission of both parents/guardians. (Permission from both parents must be obtained unless one parent/guardian is deceased, unknown, incompetent, or not reasonably available, or when only one parent/guardian has legal responsibility for the care and custody of the child). Justify reason(s) if seeking permission from only one parent.

Section 2.

In order to effectively assess and evaluate the risk of your proposed research to children, the IRB requires the following information. Respond to all items.

- a) Provide justification for the participation of children as research participants in your study.
- b) Has this research been conducted in adults?

If yes, is there any indication that the proposed research would benefit, or at least not be harmful to children?

- c) Indicate how many children you propose to enroll in the study and justify this number (whenever possible, involve the fewest number of children necessary to obtain statistically significant data which will contribute to a meaningful analysis relative to the purpose of the study).
- d) Describe how assent of a child will be obtained and documented (if applicable). If not applicable, explain why.

I am requesting waiver of the requirement for assent.

Justify:

OR

I have attached an assent form/assent script for IRB review.

e) Explain what methods will be used for evaluating dissent (i.e., description of behaviors that would indicate child does not want to participate (such as moving away, certain facial expressions, head movements, etc...).

f) Describe how parental permission will be obtained. [Note: If you propose to waive the requirement for parental permission (i.e., getting parental permission may be against the best interest of the child, i.e., a study of abused or neglected children), describe what measures will be taken to protect the rights and welfare of the children.]

I am requesting waiver of the requirement for parental permission. Justify:

OR

I have attached a parental permission form for IRB review.

- g) Describe measures that will be taken to ensure that a parent is present when the child participates in any research interventions or procedures. [Note: If the nature of the research is such that it is not appropriate to have a parent present (i.e., research into sensitive personal issues, physical examinations of teenagers, etc...) please explain why.]
- h) Describe the expertise of the research staff/study personnel for dealing with children at the ages included and whether they are knowledgeable and sensitive to the physical and psychological needs of the children and their families. Describe the appropriateness of facility in which the research will be conducted in relation to environment and/or equipment accommodating to children.

i) If applicable, provide any additional information that may support your request to involve children in this research.

* * * Subject Population(n) * * *

Research with cognitively impaired persons

NOTE: Investigators, please include this form with IRB application if your research involves cognitively impaired (decisionally impaired or decisionally challenged) persons. If your research involves people with more than one vulnerability, please complete the supplementary form for that population as well.

The IRB may ask you to designate an impartial observer to monitor the consent process or it may send its own representative to do so.

Section 1.

Note: Check the box next to the category that in your best judgment applies to your research, and provide the information requested in the space provided.

Note: Minimal risk means that the probability and magnitude of the harm or discomfort anticipated in the research are not greater in and of themselves than those ordinarily encountered in daily life or during the performance of routine physical or psychological exams
or tests. (i.e., daily life of health persons)

χ Category 1 My research does not involve greater than minimal risk.

Explain. If appropriate, describe what provisions are in place for allowing a Legally Authorized Representative (LAR) or other person with the participant's best interests at heart to assist the participant in navigating the research process:

As described in Section 2 sub-section #2 below, LARs will always be contacted and taken through a proxy consent process before NH residents with ADRD diagnoses are contacted.

Category 2 My research presents greater than minimal risk and prospect of direct benefit to the participants.

Explain. If appropriate, describe what provisions are in place for allowing a Legally Authorized Representative (LAR) or other person with the participant's best interests at heart to assist the participant in navigating the research process.

Category 3 My research presents greater than minimal risk and no prospect of direct benefit to the participants, but likely to yield generalizable knowledge about the participant's disorder or condition, because:

Explain. If appropriate, describe what provisions are in place for allowing a Legally Authorized Representative (LAR) or other person with the participant's best interests at heart to assist the participant in navigating the research process.

Category 4 My research does not fall under Category 1, 2, or 3, listed above.

If you check this category, the IRB determines additional safeguards on a case-by-case basis.

Section 2.

 Explain why individuals with impaired decision-making capacity are suitable for this research. If the objective(s) of the study allow for inclusion of competent participants, provide compelling justification for inclusion of incompetent participants.

This study does involve the vulnerable population of nursing home residents with dementia. Sleep problems and related issues in NH residents with dementia is a well-documented problem. This study implements an intervention to improve the sleep experience for these residents and increase engagement in meaningful activities. To evaluate the effects of the sleep program for people with dementia, people with dementia must be enrolled. If the LOCK sleep program is found to be effective in enhancing clinical care and outcomes, the approach can be shared with other NHs and incorporated into general NH practice. The risks in this study for NH residents are minimal, and the knowledge gained may result in improved quality of sleep, and ultimately improved quality of life for NH residents with dementia.

2. Describe who will determine individuals' competency to consent and the criteria to be used in determining competency (e.g., use of standardized measurements, consults with another qualified professional, etc...).

All consents as described below will be conducted by an IRB-approved study staff member who has been trained by [name] (principal investigator). The study staff member will be responsible for explaining the study, answering questions, and obtaining informed consent.

Cognitively Impaired NH Resident Consent – Step 1. Legally Authorized Representative Consent

NH leadership team [see Section #3B-Study Procedures] or their designees will identify all NH residents with an ADRD diagnosis and mail to their legally authorized representatives (LARs) an IRB-approved study introduction letter (including option to opt out within one month if they do not wish to be contacted by study staff). Opt-out procedures have been demonstrated to yield higher response rates and lower rates of non-response bias compared to opt-in procedures, and to be acceptable to participants, with no difference in rates of reported distress or complaints compared to opt-in procedures.[105-108] In our past federally funded research involving people with dementia, opt-out consent has been approved by multiple IRBs and worked well. Contact information of those LARs not opting out will be shared with University of Alabama (UA) study staff. We will request of the IRB a waiver of consent and HIPAA authorization for screening purposes regarding the sharing of these contact information.

Study staff will mail an IRB-approved study information packet via a tracked, express mailing service to all LARs who do not opt out. These materials will include a cover letter, an IRB-approved informed consent form (ICF), and an express mail return envelope so the LAR can send the signed ICF to the UA study office. LARs will be encouraged to contact study staff via phone or email for an appointment to discuss the study and go through the consent form together before signing the ICFs. Study staff will contact the LARs via phone and/or email within one week of sending the packet and will re-contact the LAR up to 6 times within the next month as needed to establish contact (if contact has not been established within one month, and NH staff are not able to determine that the LAR's contact information has changed, then the lack of contact will be considered a soft refusal and no other contact will be attempted).

During a phone appointment, study staff will review all important elements of the ICF with the LAR, including the following: description of the study, information on how to contact the investigators and the NH administrator and director of nursing, a statement that there is no prejudice for refusal to participate, a statement that the subject may withdraw from the study at any time without prejudice, and statement regarding risk and benefit of participation. The LAR will be encouraged to ask questions. The LAR will be encouraged to call the PI if they have any remaining questions before signing the consent form.

Cognitively Impaired NH Resident Consent – Step 2. Screening for Capacity for NH Resident Consent/NH Resident Assent

Some NH residents with mild ADRD may have the capacity to provide their own consent. For residents with likely mild ADRD and a LAR who can be contacted, a conservative two-step process will be used to address the ethical balance of the beneficence of assuring that residents who do not have the capacity to consent are protected by LAR oversight with the promotion of autonomy for residents who do have capacity to consent. Once LAR consent is received for a resident, the NH leadership team will be asked to identify that resident's most recent MDS Brief Interview for Mental Status score[120] (BIMS; see Appendix for measure), a cognitive screening measure with good reliability and validity. For residents with BIMS scores in the mild range (above 10), the NH leadership team will be asked to arrange and support a telephone appointment between that resident and a study staff person (if the resident turns out to NOT have the cognitive ability to participate in the following telephone-based procedure, then they would also NOT have the cognitive capacity to provide informed consent, which requires higher level cognitive abilities).

